 - Stratified block randomization will be used to ensure that the number of participants is equally distributed among the study groups and stratified by surgery level (major, minor). The allocation sequence will be generated with block size of 4 using computer software. Randomization will be implemented with the REDCap Randomization module. Randomization schedule can only be accessed by a research personnel not directly involved in patient care. The patient's 6-week postoperative visit will be scheduled according to her assigned group.
- Study instruments:
 - Study instruments will be administered at the preoperative visit and the 6-week postoperative visit. The questionnaires for this study include the Patient Preparedness Questionnaire (PPQ), the Patient Satisfaction Questionnaire-18 (PSQ-18), and modified patient and provider preference questionnaires entitled, Patient Postoperative Visit Questionnaire and Provider Postoperative Visit Preference Questionnaire.
 - The PPQ will be administered during the preoperative visit to assess patient knowledge and preparedness for surgery, which has been demonstrated in other studies to impact postoperative satisfaction, perceived complications, and drug utilization.¹⁰⁻¹¹ The PPQ is a 11-item questionnaire scored on a six-point Likert scale and has responses ranging from 1 (strongly agree) to 6 (strongly disagree).⁹ The questionnaire for this study will utilize the same six-point scale with a reversed scoring system, ranging from 1 (strongly disagree) to 6 (strongly agree). Although there are currently no validated measures to assess surgical preparedness in urogynecology, the PPQ has been used in several studies assessing surgical preparedness in women undergoing pelvic organ prolapse and/or stress urinary incontinence.^{8,12} These studies utilized the same cutoff score for question 11 (i.e., an answer of "strongly agree" to the question "overall, I feel prepared for my upcoming surgery") to define meeting criteria for preoperative preparedness.
 - The PSQ-18 will be administered after the 6-week postoperative virtual or in-office visit to assess patient satisfaction with their postoperative visit. The PSQ-18 is a

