- All questionnaires can be completed either with paper forms or electronically through Research Electronic Data Capture (REDCap), depending on patient/provider preference. Study participants will be reminded within 48 to 72 hours after their visit regarding completion of their questionnaires by telephone call using a standardized phone script or by text or email message after their preoperative visit and their 6-week postoperative visit. Reminders for survey completion will be sent up to two times.

- Preoperative Visit
 - The preoperative visit will take place per our standard protocol, which includes a thorough discussion of the surgical purpose, alternatives, benefits, risks/complications, and postoperative expectations. Following informed consent, study-related procedures during the preoperative visit include study randomization, and scheduling of postoperative visits per study protocol. The PPQ will also be administered during this visit.
- Postoperative Visit (6 weeks)
 - Prior to the 6-week postoperative visit, a study investigator will initiate a reminder to the participant by phone, email or text to remind her of her upcoming appointment using a standard script. A checklist of discussion points will be used to standardize counseling and evaluation during the 6-week postoperative visit. Both office and virtual visits will be conducted in the same manner: The provider

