- Emergency department or urgent care visits during the next six weeks following the scheduled 6-week postoperative visit (Y/N); if Y,
 - Total number of ED/urgent care visits (No. of occurrences)
 - Date of ED visit #1 (MM/DD/YYYY)
 - Reason/s for ED visit
 - Outcome of ED visit (discharge, readmission, reoperation, other-specify)
 - Date of ED visit #2 (MM/DD/YYYY)
 - Reason/s for ED visit
 - Outcome of ED visit (discharge, readmission, reoperation, other-specify)
- Hospital readmissions during the next six weeks following the scheduled 6-week postoperative visit (Y/N); if Y,
 - Total number of hospital readmissions
 - Date of readmission #1
 - Reason/s for readmission
 - Outcome of readmission (discharge, reoperation, other-specify)
 - Hospital length of stay (no. of days)
- Adverse events during the next six weeks following the scheduled 6-week postoperative visit (Y/N); if Y, specify (urinary tract infection, neurologic injury, hemorrhage/hematoma, blood transfusion, wound infection and cellulitis, seroma, abscess, pyelonephritis, sepsis, vaginal fistula, vaginal dehiscence, deep venous thrombosis, pneumonia, drainage of abscess, delayed gastrointestinal injury, delayed genitourinary injury, ileus, small bowel obstruction, pulmonary embolism, myocardial infarction, cerebrovascular accident and stroke, death, mesh complication, readmission, reoperation)
- Power Analysis and Sample Size Calculation
 - The primary outcome of this study is to compare patient satisfaction between patients scheduled for office versus virtual six-week postoperative visits.
 - A priori sample size calculation determined that 100 participants (50 per group) would allow for 80% power to assess a noninferiority margin of 5 points on the

total PSQ-18, with a SD of 10 and significance level of 0.05. A minimum important difference has not been reported for the PSQ-18; however, previous studies using this tool demonstrated SD for total PSQ-18 score ranging between 2.6 and 11.8 and used a 5-point interval for the noninferiority margin.^{6,13} To account for an anticipated attrition rate of approximately 5%, we aimed to enroll a total of 106 participants (53 per group).

- **Statistical Analysis**

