- Patient satisfaction (PSQ-18) total scores, as well scores in each of the 7 PSQ-18 domains, will be treated as continuous data and checked for normality. Healthcare utilization will be analyzed individually (number of phone calls, number of outpatient visits, number of emergency department or urgent care visits, number of hospital readmissions), as well as a composite of all encounter types. Adverse events will be analyzed independently but also as a composite utilizing the Clavien-Dindo Grading System for surgical complications. Attitudes toward office/virtual visits will be analyzed by comparing proportions of patients and providers who prefer a virtual visit, prefer an office visit, or have no preference.
- All analyses will be conducted using an intention-to-treat principle. Baseline demographic and clinical characteristics will be summarized using descriptive statistics. Normally-distributed continuous measures will be summarized using mean and standard deviation (SD), whereas those showing departure from normality will be summarized using median and interquartile range (IQR). Categorical measures will be summarized using number of participants and percentage. The primary end-point analysis will be designed to test whether patient satisfaction with a virtual postoperative visit is noninferior to an in-person postoperative visit, as determined by the total PSQ-18 at the scheduled postoperative visit. Noninferiority would be shown if the lower limit of the two-sided 95% confidence interval for the between-group mean difference in the primary endpoint (i.e., the difference between the mean PSQ-18 total score in the virtual group minus the mean PSQ-18 total score in the in-office group) is more than -5 points. Similar analyses will be performed for each secondary outcome. The noninferiority margin is defined as 5 points for the PSQ-18 total score and 0.5 points for the PSQ-18 domain scores, 10% absolute for composite healthcare resource utilization, and 25% absolute for composite adverse events. Planned exploratory subgroup analyses of patient satisfaction, healthcare resource utilization and adverse events based on surgery level will be additionally performed.
- All statistical analyses will be performed using JMP Pro version 17.0 software (SAS Institute, Cary, NC).
- Data will be managed in REDCap. Statistical support will be provided by the Cleveland Clinic Quantitative Health Sciences.

E. PRIVACY AND CONFIDENTIALITY

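### The preparedness score is collected from every participant but left out of the primary comparison, and nothing requires it to be completed before randomization, so some precision, of unknown size, is given up

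*Combined protocol and SAP*

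**What the plan says.** Under Study instruments (section C), the protocol says the PPQ assesses knowledge and preparedness for surgery, "which has been demonstrated in other studies to impact postoperative satisfaction". The background section likewise reports a positive correlation between preparedness and postoperative satisfaction. No size is given in either place. The schedule of procedures puts the PPQ at the preoperative visit for all participants, and $10 of the compensation is tied to it.

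On timing, the Preoperative Visit section says "Following informed consent, study-related procedures during the preoperative visit include study randomization, and scheduling of postoperative visits per study protocol", followed by "The PPQ will also be administered during this visit". No sentence sets an order between the questionnaire and randomization. The Randomization section has the six-week visit booked according to the assigned group, so the patient can learn her arm at the preoperative visit. Questionnaire reminders, up to two, go out 48 to 72 hours after that visit.

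On analysis, the Statistical Analysis section defines the primary estimate as "the difference between the mean PSQ-18 total score in the virtual group minus the mean PSQ-18 total score in the in-office group" and compares the lower limit of its two-sided 95% confidence interval with -5. It names no covariate. The PPQ appears neither in that section nor in the data lists of section D.

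**The concern.** A baseline score that predicts the primary outcome can narrow the noninferiority interval and correct a chance imbalance between arms at no cost in patients. Here the plan itself presents such a score, pays for it and sends reminders for it, and then gives it no role in the comparison it could sharpen.

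The timing matters because it decides whether the score could be used safely. A covariate has to be unaffected by allocation. In an open-label trial, a PPQ answered after the follow-up visit has been booked is no longer strictly a baseline measure. If knowing the arm changed the answers, adjusting for them would remove or add part of the arm difference. The two points therefore belong together: the PPQ should precede allocation, and its use should be written down before the data are seen.

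**Working it through.** **Inputs from the documents.** Margin 5 points and power 80% ("80% power to assess a noninferiority margin of 5 points"); "with a SD of 10 and significance level of 0.05"; 50 evaluable per arm and 106 enrolled (Power Analysis and Sample Size Calculation). Decision rule: lower limit of the two-sided 95% interval above -5 (Statistical Analysis).

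**Assumptions.** True difference 0. The PPQ/PSQ-18 correlation r is not in the documents, so 0.1 to 0.4 is shown.

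**1. The plan's own figure.** By the normal approximation, n per arm = 2 × SD² × (z for alpha + z for power)² / margin².
- One-sided 0.05: 2 × 100 × (1.645 + 0.842)² / 25 = 49.5, so 50 per arm. This matches the plan. Allowing for 5% attrition, 100 / 0.95 = 105.3, which is 106 with equal arms.
- One-sided 0.025, which is what a two-sided 95% interval implies: 2 × 100 × (1.960 + 0.842)² / 25 = 62.8, so 63 per arm. This does not match.

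The stated size therefore fits one-sided 0.05, while the analysis rule is stricter. This is a separate issue, and it explains why the starting power below is about 70% and not 80%.

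**2. Effect of adjusting for the PPQ.** Residual SD = 10 × √(1 − r²). Standard error = residual SD × √(2/50). Half-width = t(0.975) × standard error, with 98 degrees of freedom unadjusted and 97 with the PPQ. Power is from the noncentral t distribution with noncentrality 5 / standard error.

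Example, r = 0.3: residual SD = 10 × √0.91 = 9.54; standard error = 9.54 × 0.2 = 1.908; half-width = 1.985 × 1.908 = 3.79.

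| r | Residual SD | Half-width, 95% interval | Power, two-sided 95% interval | Power, one-sided 0.05 |
|---|---|---|---|---|
| Unadjusted | 10.00 | 3.97 | 69.7% | 79.9% |
| 0.1 | 9.95 | 3.95 | 70.1% | 80.2% |
| 0.2 | 9.80 | 3.89 | 71.4% | 81.3% |
| 0.3 | 9.54 | 3.79 | 73.7% | 83.1% |
| 0.4 | 9.17 | 3.64 | 77.1% | 85.6% |

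By the normal approximation, r would have to be about 0.45 for 50 per arm to reach 80% power under the two-sided 95% interval.

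**3. Chance imbalance.** With 50 per arm, the standardized PPQ difference between arms has standard error √(2/50) = 0.2. An imbalance of two standard errors (0.4 SD) at r = 0.3 would move the unadjusted estimate by 0.3 × 0.4 × 10 = 1.2 points. This is part of the ordinary sampling error that the unadjusted interval already covers; adjustment would remove it.

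**4. Why the order matters if the PPQ is used.** Suppose knowing the arm shifted the PPQ by 0.2 SD. Adjusting at r = 0.3 would then move the estimate by about 0.3 × 0.2 × 10 = 0.6 points against a 5-point margin. The 0.2 SD is illustrative; the documents give no evidence of any shift.

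**The case against.** The strongest reply is that no planned analysis is harmed. A randomized difference in means needs no covariate, and the timing of the PPQ could cause bias only under an adjustment the plan does not make. This stands. A reader might infer that the primary comparison is biased, and the documents do not support that.

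A reader might also infer that PPQs will be collected after assignment. The text leaves the order open. Late completion is possible because of the reminders, but how often it would occur is unknown, and nothing suggests that knowing the mode of a six-week visit changes how ready a patient feels for surgery.

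The predictor may also be weak. The cited link is to postoperative satisfaction in general, whereas the PSQ-18 here measures satisfaction with the visit and includes finances and convenience. The protocol also says no validated preparedness measure exists in urogynecology. A correlation of 0.1 is as compatible with the documents as 0.4, and at 0.1 the gain is negligible. This also stands, and it is why a range is shown and no single figure is claimed.

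Finally, the plan never promises to use the PPQ as a covariate; its stated purpose is to assess preparedness. That is fair, but the analysis text gives the score no named use at all. The objection reduces the weight of the point without removing it, because the downside of adjusting is so small.

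**Conclusion.** The point holds as an improvement in efficiency, not as an error of validity. The plan collects a score that it describes as related to satisfaction, does not use it in the primary comparison, and does not secure its completion before allocation. Under the written two-sided 95% rule, the power given up is about 0.4 percentage points at r = 0.1, 1.7 at r = 0.2, 4.0 at r = 0.3 and 7.4 at r = 0.4. This rests on SD 10, 50 evaluable per arm, no true difference, and a correlation the documents do not give.

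The table should not be read as showing that the missing covariate causes the power shortfall. Starting power near 70% reflects sizing at one-sided 0.05 and analysis with a two-sided 95% interval. Adjustment at the correlations shown offsets only part of that gap, which needs its own resolution.

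**What to change.** - **Preoperative Visit section:** state that the PPQ is completed before the REDCap randomization module is opened, with any PPQ reminders sent before allocation.
- **Statistical Analysis section:** prespecify a linear model of PSQ-18 total on arm, surgery level (the randomization stratum) and continuous PPQ score. Judge the two-sided 95% interval for virtual minus in-office against -5. Keep the unadjusted difference as a sensitivity analysis. Define the PPQ score in advance, and use a simple mean fill only for PPQs with skipped items, since under the first change no randomized patient should lack the questionnaire altogether.

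**Cost.** The PPQ term uses one degree of freedom. If r is near zero, power at 50 per arm falls by well under 1 percentage point. No patients, visits or instruments are added. The practical cost is that randomization and scheduling may wait briefly for the PPQ. Where a patient prefers to complete it electronically after the visit, both would move to after the visit, and a consented patient who never returns it would not be randomized. The sponsor should decide in advance how to handle that.

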- All patients of the Center for Urogynecology and Pelvic Reconstructive Surgery in the Department of Obstetrics/Gynecology and Women's Health Institute at the Cleveland Clinic (Main Campus, Fairview Hospital, Hillcrest Hospital, Medina Hospital and Beachwood Ambulatory Surgery Center) scheduled to undergo major or minor surgery for pelvic organ prolapse and/or urinary incontinence
 - Major surgery⁺
 - Minimally invasive (laparoscopic or robotic) sacrocolpopexy
 - Vaginal colpopexy (intraperitoneal or extraperitoneal)
 - Vaginal or minimally invasive (laparoscopic or robotic) hysteropexy (uterine suspension)
 - Obliterative procedures (colpocleisis)
 - Additional procedures accompanying the above major operations may include: hysterectomy (total or supracervical), trachelectomy, salpingectomy or salpingo-oophorectomy, anterior and/or posterior colporrhaphy with perineorrhaphy, enterocele repair, minimally invasive Burch colposuspension or paravaginal defect repair, vaginal mesh removal or revision, placement of vaginal graft, or placement of mid-urethral sling
 - Minor surgery
 - Isolated colporrhaphy (anterior/posterior) and/or perineorrhaphy
 - Placement of mid-urethral sling
 - Vaginal mesh removal or revision
- Inclusion Criteria
 - Age greater than 18 years old
 - Has technological capability to participate in videoconferencing (high-speed internet access with desktop computer or mobile device)
 - Has decision-making capacity and able to provide informed consent for research participation
 - Able to speak and read English
- Exclusion Criteria
 - Patient requested to physically come in the office or have a virtual visit for her postoperative visit
 - Planned concomitant surgery with another surgical team
 - Office follow-up is deemed medically necessary by provider/surgeon

Study Procedures

- Screening and Recruitment
 - Participants will be prospectively identified by the primary surgeon during the patient's initial consultation when the decision is made to proceed with surgery for pelvic organ prolapse and/or urinary incontinence.

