 - Compensation will be provided to trial participants with a total of \$50 in the form of a check in the mail from Cleveland Clinic. The payment will be prorated according to the procedures completed. The participant will receive \$10 after completion of the Patient Preparedness Questionnaire pre-operatively, \$20 after completion of the Patient Satisfaction Questionnaire-18 postoperatively, and \$20 after completion of the Patient Postoperative Visit Questionnaire postoperatively. Addresses for mailing of checks will be verified.
 - Reasons for declining participation in the study will be collected and recorded separately.

- Consent/Accent Process
 - Patients who agree to participate will sign a consent form. The consent interview will occur during the participant's preoperative visit at the Center for Urogynecology and Pelvic Reconstructive Surgery at Cleveland Clinic. Alternatively, the patient will be able to provide consent for research participation remotely via electronic signature using the DocuSign eConsent Platform.
- Randomization:
 - Trial participants will be randomized to one of two arms:
 - 1) **Office Visit (Control Arm):** Patients randomized to the control arm will be scheduled for and follow up with the surgeon or an advanced practice provider via an in-office visit at 6 weeks after the planned date of surgery. If the surgery were to be rescheduled to a future date, the postoperative visit will be moved accordingly to ensure follow-up occurs at the 6-week postoperative period.
 - 2) **Virtual Visit (Intervention Arm):** Patients randomized to the intervention arm will be scheduled for and follow up with the surgeon or an advanced practice provider via a virtual visit using videoconference technology at 6 weeks after the anticipated date of surgery. If the surgery were to be rescheduled to a future date, the postoperative visit will be moved accordingly to ensure follow-up occurs at the 6-week postoperative period.

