 - Marital status
 - Distance from home to clinic (miles)
 - Vaginal parity
 - Menopausal state
 - Current tobacco use (Y/N)
 - BMI (kg/m²)
 - Comorbid conditions (MI, CHF, peripheral vascular disease, cerebrovascular disease, dementia, chronic pulmonary disease, connective tissue disease, ulcer disease, mild liver disease, diabetes, diabetes with end organ damage, hemiplegia, moderate or severe renal disease, any tumor without metastasis, leukemia, lymphoma, moderate or severe liver disease, metastatic solid tumor, AIDS)
 - Charlson Comorbidity Index (CCI) score
 - *Calculation for CCI: diabetes with complications, hemiplegia/paraplegia, renal disease, and malignancies, age 60-69 are assigned a score of 2; age 70-79 moderate/severe liver disease is assigned a score of 3; metastatic solid tumour and AIDS/HIV are assigned a score of 6; the remaining comorbidities are assigned a score of 1*
 - Prior prolapse surgery (Y/N; if Y, specify)
 - Prior anti-incontinence surgery (Y/N; if Y, specify)
 - Preoperative prolapse overall stage based on POP-Q exam (0, I, II, III, IV)
 - Preoperative POP-Q points (Aa, Ba, C, GH, PB, TVL, Ap, Bp, D)
 - Preference for text or email reminder communication
 - Preferred mobile phone number or email address
- B) Perioperative data will include the following:
 - Date of surgery (MM/DD/YYYY)
 - Location of OR facility
 - Surgery level (Minor, Major)
 - Surgery type
 - Concomitant procedures
 - Operative time (minutes)
 - Estimated blood loss (ml)
 - Intraoperative complications (bladder injury, ureteral kinking, bowel injury, vascular injury, EBL ≥300 ml, transfusion, conversion to open procedure, other-specify)
 - Hospital length of stay (no. of hours if <24 hours; no. of days if >24 hours)
 - If patient was admitted, was the admission planned (Y/N)

- If N, specify reason for postoperative admission
- Voiding trial results (Pass/Fail)
 - If Fail, select outcome: foley catheter reinserted, patient taught intermittent self-catheterization
- Postoperative prescriptions at discharge (name, dosing, quantity)

○ C) Six-week postoperative data will include the following:

- Date of postoperative visit (MM/DD/YYYY)
- Number of days postop at 6-week visit
- Route of postoperative visit (in-office, virtual)
 - If virtual, was an in-office visit recommended for further evaluation (Y/N); reason for office evaluation (specify)

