 - If virtual, did the patient require assistance with using video conference technology prior to their scheduled appointment (Y/N)
 - If virtual, were there any technological difficulties during the visit (Y/N)
- Did the patient cross-over to the other group at any point before the 6-week visit (Y/N)?
- Provider conducting postoperative visit (APRN, MD, other-specify)
- Abdominal exam performed (Y/N); if Y, list findings (normal, abnormal-specify)
- Pelvic/vaginal exam performed (Y/N); if Y, list findings (normal, abnormal-specify)
- Patient-initiated phone call to surgeon's office prior to 6-week postoperative visit (Y/N); if Y,
 - Total number of phone calls (No. of occurrences)
 - Date of phone call #1 (MM/DD/YYYY)
 - Reason/s for phone call #1
 - Outcome of phone call (counseling/reassurance, prescription sent, new order placed, new office/virtual appointment scheduled, advised to go to ED/urgent care, provider placed follow-up call to patient the next day, other-specify)
 - Date of phone call #2 (MM/DD/YYYY)
 - Reason/s for phone call #2
 - Outcome of phone call
 - Date of phone call #3 (MM/DD/YYYY)
 - Reason/s for phone call #3
 - Outcome of phone call
- Unanticipated outpatient (office/virtual) visits to surgeon's office prior to 6-week postoperative visit (Y/N); if Y,
 - Total number of outpatient visits including office voiding trials (No. of occurrences)
 - Total number of voiding trial visits (No. of occurrences)
 - Date of outpatient visit #1 (MM/DD/YYYY)
 - Reason/s for outpatient visit
 - Outcome of outpatient visit (counseling/reassurance, prescription sent, new order placed, new office/virtual appointment scheduled, advised to go to ED/urgent care, hospital/direct admission, reoperation, provider/patient to place follow-up call, other-specify)

- Date of outpatient visit #2 (MM/DD/YYYY)
 - Reason/s for outpatient visit
 - Outcome of outpatient visit
 - Date of outpatient visit #3 (MM/DD/YYYY)
 - Reason/s for outpatient visit
 - Outcome of outpatient visit
- Emergency department or urgent care visits prior to 6-week postoperative visit (Y/N); if Y,
 - Total number of ED/urgent care visits (No. of occurrences)
 - Date of ED visit #1 (MM/DD/YYYY)
 - Reason/s for ED visit
 - Outcome of ED visit (discharge, readmission, reoperation, other-specify)
 - Date of ED visit #2 (MM/DD/YYYY)
 - Reason/s for ED visit
 - Outcome of ED visit (discharge, readmission, reoperation, other-specify)

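### Randomization before surgery leaves later medical reasons for office follow-up without a rule; any resulting virtual-to-office switching could dilute the intention-to-treat comparison toward noninferiority

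*Combined protocol and SAP*

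**What the plan says.** - **Timing.** Section C, Preoperative Visit: after consent, "study-related procedures during the preoperative visit include study randomization, and scheduling of postoperative visits per study protocol". The Randomization text adds that the 6-week visit is booked by assigned arm, with stratification by major or minor surgery. At that point only the planned level can be known.
- **Arms.** They differ in the mode of the 6-week visit. The visit is otherwise to be conducted in the same way in both.
- **Eligibility.** Two exclusion criteria bear on visit mode: "Office follow-up is deemed medically necessary by provider/surgeon" and "Patient requested to physically come in the office or have a virtual visit for her postoperative visit". Neither has a stated time of application, and nothing says what follows if one becomes true after randomization.
- **Changes to the operation.** "If the surgery were to be rescheduled to a future date, the postoperative visit will be moved accordingly". A cancelled operation is not mentioned.
- **Data collected.** Section D records intraoperative complications, voiding trial results, unplanned admission and postoperative adverse events. The six-week form records the route of the visit, a yes/no item for crossover before the visit (either direction, no reason), and whether an office visit was advised after a virtual one.
- **Analysis.** "All analyses will be conducted using an intention-to-treat principle". No per-protocol or as-treated analysis, expected crossover rate or handling of crossover is given.

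**The concern.** Allocation is fixed before the operation, while the compared treatment is delivered six weeks after it. At enrolment the medical-necessity exclusion can screen only for what is already known. Some events on the plan's own forms, such as an intraoperative injury or a failed voiding trial, become known later and could plausibly lead a surgeon to want an office visit. In the virtual arm that would mean a switch; in the office arm it would change nothing. Switching for this reason therefore has only one possible direction.

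Under intention to treat, a virtual-arm patient seen in the office counts as virtual. If her score resembles an office patient's, the observed difference moves toward zero. In a superiority trial that is usually conservative. In a noninferiority trial it helps the claim. The unstated alternative, applying the exclusion after randomization, would instead remove patients selectively from one arm.

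**Working it through.** **1. The plan's own figure.** Inputs from the sample size section: margin 5, SD 10, 80% power, significance level 0.05.

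n per group = 2 × SD² × (z₀.₉₅ + z₀.₈₀)² / margin² = 2 × 100 × (1.645 + 0.842)² / 25 = 49.5, rounded up to 50. With 5% attrition, 100 / 0.95 = 105.3, rounded up to 106 (53 per group). The stated figures reproduce with a one-sided 0.05. The decision rule uses the two-sided 95% interval, which is one-sided 0.025, so that level is used below. The mismatch is a separate matter.

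**2. Dilution model.** Let c be the fraction of the virtual arm seen in the office and d the true effect of visit mode. If switchers score like office patients:

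- intention-to-treat difference = (1 − c) × d
- SE = 10 × √(2/50) = 2.0
- P(noninferiority declared) = Φ((5 + difference)/SE − 1.96)

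The plan gives no value for c, so a range is assumed. With d = −5, exactly at the margin:

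| c | Switchers out of 50 | Difference | False noninferiority |
|---|---|---|---|
| 0% | 0 | −5.00 | 2.5% |
| 5% | 2.5 | −4.75 | 3.3% |
| 10% | 5 | −4.50 | 4.4% |
| 20% | 10 | −4.00 | 7.2% |

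For c = 10%: (5 − 4.5)/2 − 1.96 = −1.71, and Φ(−1.71) = 0.044.

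**3. What moves the result.**

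- *SD.* The plan quotes 2.6 to 11.8 from earlier studies. At c = 10%, SD 11.8 (SE 2.36) gives 4.0% and SD 2.6 (SE 0.52) gives 15.9%.
- *Switching both ways.* With 10% in each direction, the difference is (1 − 0.1 − 0.1) × (−5) = −4.0, giving 7.2%.
- *Switchers who would have done worse on video.* If their deficit is twice that of the others and the overall effect is still −5, then at c = 10% the others' effect is −5/1.1 = −4.545. The difference is 0.9 × (−4.545) = −4.09, giving 6.6%.
- *A cost of switching itself.* If switchers score q points below office counterparts, the difference is −5(1 − c) − cq. At q = 5 it is −5 for every c, and the error returns to 2.5%. At q = 8 and c = 10% it is −4.5 − 0.8 = −5.3, giving 1.7%, which is conservative.
- *No true effect.* With d = 0 the difference is 0 for every c.

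**4. Cancelled operations.** These patients have no 6-week visit and hence no PSQ-18 score. Nothing in the documents makes cancellation depend on arm. They use up the 6 participants allowed for attrition (106 − 100), so they cost precision.

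**5. Dropping switchers.** If such patients score m points lower in either arm and are removed only from the virtual arm, that arm gains c × m. At c = 10% and m = 5 to 10, this is 0.5 to 1.0 points, again in favor of noninferiority.

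**The case against.** The strongest reply is that the trial may be comparing booking policies. The sample size section describes patients scheduled for each type of visit. Under that reading, conversion to an office visit is part of the virtual strategy and intention to treat answers the question without bias. This is a fair reading, but the primary aim speaks of patients receiving each type of visit, and the plan does not choose between the two.

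A reader might also infer that the design makes one-way crossover certain, that reasons for office follow-up mostly arise at or after surgery, and that the result is therefore biased toward noninferiority. The documents do not support this:

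- They give neither reasons nor timing for medical necessity. Comorbidity or the planned operation could trigger it before randomization.
- They do not link complications to visit mode. Unscheduled outpatient visits, including office voiding trials, are recorded separately, so a complication can be seen there while the 6-week visit stays virtual. An office visit advised after a virtual one leaves that visit virtual.
- The crossover item covers both directions, and the patient-request exclusion names both modes.
- The direction of bias depends on how switchers score.

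Nor do cancelled operations favor noninferiority. The objection also rightly notes that later randomization is only a partial remedy, since wound infection, dehiscence or reoperation may follow discharge.

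What survives is the gap itself: early allocation, no rule for later medical necessity, and a single analysis that cannot show how much switching mattered.

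**Conclusion.** The point holds conditionally. Randomization comes earlier than the comparison needs, and the plan is silent on medical necessity that emerges afterwards. Any switching on that ground would run from virtual to office and, if switchers score like office patients, would dilute a true deficit. At SD 10 the effect on the error rate is modest at 5% switching (2.5% to 3.3%) and nearly triples it at 20% (7.2%). These figures assume 50 analyzed per arm and a true deficit exactly at the 5-point margin. They are a range over an unknown rate and do not predict what this trial will see. The change is worth making because it is inexpensive and removes an avoidable part of the problem.

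**What to change.** 1. Keep consent and the PPQ at the preoperative visit. Move REDCap randomization to after surgery, at discharge and before the 6-week visit is booked. Amend the Preoperative Visit and Randomization text to match.
2. Before the arm is revealed, have the surgeon confirm in REDCap that the existing exclusion criteria still do not apply. Stratify on the surgery level performed.
3. Keep the crossover item, because events after discharge can still cause switching. Add a reason field, and report crossover by arm and reason.
4. Prespecify a supporting analysis by visit mode received, beside the intention-to-treat analysis. Switchers should not simply be dropped from one arm. One form that keeps everyone divides the intention-to-treat difference by the between-arm difference in the proportion seen virtually. In the 10% row above, −4.5 / 0.9 = −5. It assumes that switching itself does not alter the score, which should be stated.

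**Cost.** A protocol amendment; a changed booking step across the five listed surgical locations; a few consented patients who are never randomized; and a slightly narrower population, which also applies to the utilization and adverse-event comparisons. No visit is added. Steps 1 and 2 remove cancelled operations and reasons known by discharge from the randomized set; steps 3 and 4 address what remains.
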